## B. DSM Procedures

### B1. Monitoring study safety.

Monitoring schedule. All the stimulation and testing sessions will be supervised by trained research staff who will monitor potential adverse events and symptoms. At each stimulation, participants will be asked to report any adverse events they have experienced. A study physician (i.e., [name]) will also be available to evaluate the participant if needed. Based on information obtained at this visit, participants will then be referred for follow-up assessment and/or treatment with the appropriate healthcare provider. Drs. [name], [name], [name], and [name] will meet every month (by phone and/or in person) to monitor study progress including data collected from participants on any serious health events that caused them to seek medical attention and if any of these resulted in hospitalizations overnight. Any adverse reactions noted by any of the team members will be reported to the PI, the UTHealth IRB, SMC, and NINR. All adverse events will be reviewed monthly by the research team and annually by the SMC. Also, in keeping with NIH guidelines, minority status and gender will be included in these reports to allow for the detection of differential effects.

Auditing selected cases for compliance with IRB requirements. All data designated as primary outcome data will be subject to a 100% cross-referencing between electronic and paper forms. This audit must have an error rate less than 1%. If the verification fails the audit, all data will be re-entered, the original computer files will be discarded, and the newly re-entered data will be audited. This process will continue until the audit no longer exceeds the maximum allowable error rate. All audits will be supervised and documented by the PI.

Conformance with informed consent requirements. This study will be approved by the UTHealth IRB and registered on ClinicalTrials.gov, and written informed consent will be obtained from all participants prior to study commencement. The informed consent document will thoroughly describe the procedures and any associated risks, and study staff will verbally review the information with each participant before enrollment into the protocol. They will also be informed that they can withdraw their consent at any time without penalty. Individuals will participate in the study only after they provide verbal and signed consent. Consent will be obtained by trained research personnel in a private space. The informed consent form will be reviewed in detail with each potential participant, and they will be provided a copy of the informed consent form to review prior to providing consent. Informed consent will be documented in writing via the participant's and investigator's signatures.

Verification of source documents. A number of quality control procedures will be used to ensure the validity and integrity of the data and the safety of all participants involved in the study. Relevant data and safety information obtained from each study participant will be verified against the original source documents by the study coordinator, and any identified discrepancies will be reviewed at these weekly meetings. All identifying information will be archived on a password-protected server in password-

protected folders and files. Only study staff will have access to these files. We will use the double data entry module in REDCap for self-report data. Computer-generated reports of variable frequencies and participant lists will be reviewed, leading to possible corrections to coding or entry. After data within a given group are checked for accuracy, the data will be stored in the password-protected folders.

Investigator compliance. All of investigators will complete Protection of Human Subjects certification and receive additional education on research and ethics as needed.

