# Self-Administered Transcranial Direct Current Stimulation for Pain in Older Adults With Knee Osteoarthritis: A Phase II Randomized Sham-Controlled Trial

NCT04016272  
November 7, 2019

Protocol Title:	Self-Administered Transcranial Direct Current Stimulation for Pain in Older Adults with Knee Osteoarthritis: A Phase II Randomized Sham-Controlled Trial
Principal Investigator:	[name]
Co-Investigators:	[name] [name] [name], PhD
Study Coordinator:	[name]
Population:	A maximum of 120 community-dwelling older adults with knee osteoarthritis who are 50–85 years old in Southeast Texas will be enrolled. Participants who meet eligibility criteria will be randomly assigned to either active tDCS (n = 60) or sham tDCS (n = 60).
Number of Sites:	UTHealth School of Nursing is the only site for this study.
Study Duration:	Three years
Subject Duration:	Four months including follow-up assessments

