## Study Design

- We will conduct a double-blind (participant and experimenter), randomized, sham-controlled, phase II parallel-group study with two groups (sham and active tDCS) in 120 older adults with knee OA.
- Expected duration of study is three years after the IRB approval from CPHS.
- tDCS with a constant current intensity of 2 mA will be applied for 20 minutes per session daily for 2 weeks (Monday to Friday) via the Soterix 1x1 tDCS mini-CT Stimulator device (Soterix Medical Inc., NY; 6.5 inches long, 3 inches wide, 0.7 inches thick) with headgear and 5x7 cm saline-soaked surface sponge electrodes. The FDA has ruled that the aforementioned tDCS stimulator is a “non-significant risk” device, a requirement for Investigational Device Exceptions. The sponge electrodes snap into the custom headgear, which is secured to the participant’s head for simple and fail-safe electrode preparation. This single-position headgear with clearly labeled sponge markers eliminates room for user error and helps conserve the placement of the montage. Participants can only administer a stimulation session via the Soterix 1x1 tDCS mini-CT Stimulator device after being provided a single-use unlock code by the research staff once proper contact quality is achieved (only the on/off button will be adjustable by the study participants; they will not be able to adjust the device settings). After the participant enters the unlock code, the screen on the device will show a timer that counts down the minutes until the end of the session. At 20 minutes, the device will turn off automatically, and study staff will instruct the participant to remove the headset and discard the sponges and to safely store all materials for the next session. For sham stimulation, the electrodes will be placed in the same positions as for active stimulation, but the stimulator will only deliver 2 mA current for 30 seconds. This sham stimulation method has been shown to be reliable and indistinguishable from active treatment.

[figure not shown]

Figure 1. Study flow diagram

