### Study Procedures

- Participants will do self-administered tDCS at their home or private room for three weeks (Mondays-Fridays) under real-time supervision by the research staff. Data will be collected by study staff across several points using equipment and resources available at [name] (PI's) laboratory at UTHealth School of Nursing (see Table below). Participants will visit UTHealth School of Nursing four times, and each visit will take approximately 2 hours.

Stimulation Session	B	Week 1					Week 2					Week 3					M1	M2	M3	
		1	2	3	4	5	6	7	8	9	10	11	12	13	14	15				
Pregnancy Test	X																			
MMSE	X																			
Knee Radiograph*	X																			
Medical History Questionnaire	X																			
Clinical Pain Intensity																				
NRS (primary outcome)	X	X	X	X	X	X	X	X	X	X	X	X	X	X	X	X	X	X	X	
WOMAC (secondary outcome)	X					X					X						X	X	X	X
PCS (secondary outcome)	X					X					X						X			
Pain-related Cortical response																				
fNIRS imaging (secondary outcome)	X					X					X						X			
QST measures	X					X					X						X			
Feasibility and Acceptability																				
tDCS experience questionnaire (secondary outcome)																	X			
Side effects questionnaire (secondary outcome)		X	X	X	X	X	X	X	X	X	X	X	X	X	X	X				

Note: B, Baseline; M, Monthly follow-up phone assessment after completion of tDCS treatment; MMSE, Mini-Mental Status Exam; NRS, Numerical Rating Scale; WOMAC, Western Ontario and McMaster Universities Osteoarthritis Index; PCS, Pain Catastrophizing Scale; QST, Quantitative Sensory Testing; fNIRS, functional near-infrared spectroscopy. The baseline visit will occur 3 to 7 days prior to the tDCS intervention, and will include medical history questionnaire, clinical pain intensity, and fNIRS imaging. Each month for three months post-intervention, participants will complete a follow-up telephone

assessments of clinical pain intensity. \* Knee radiographs can be scheduled at a different time depending on the participants' availability.

- Pregnancy Test. If participants are a woman of childbearing potential, there may be unknown risks to the fetus. Therefore, pregnancy test by a sample of urine will be obtained in all woman of childbearing potential once at baseline visit.
- MMSE. MMSE will be used to exclude people with diminished cognitive function (i.e., Mini-Mental Status Exam score  $\leq 23$ ).

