Adverse event reporting. Study participants will be encouraged to immediately report any "emergencies or events" by calling the study contact number. These instructions will be included on the consent forms. The study team will record all reported events in the adverse events and unanticipated problems log (including the subject's name, the date, and an event description). All members of the study team will inform the PI, [name], immediately of any adverse events and unanticipated problems, and he will consult with co-investigators and the SMC members on the necessary action. The PI will report the incident to the UTHealth IRB within one week. The action and date of implementation will also be recorded in the adverse events and unanticipated problems log. The entire investigative team and SMC will participate in classifying events as "serious" or "non-serious" (see list below), as well as "non-attributable," "possibly attributable," or "attributable" to the intervention. The SMC will advise the PI and the study team on actions to be taken to minimize further adverse events and unanticipated problems within 2 weeks of reviewing the reports.

1. Serious events include any event or condition that is life threatening or results in a hospitalization or a physical or cardiac event serious enough to require medical attention. These events may be:

- a. Fatal
- b. Life threatening

- c. Permanently disabling
- d. Required or prolonged hospitalization (admission, not ER visit)
- e. Overdose
- f. Significant hazard to the patient

2. Non-serious events include all other events.

D. This is a single site study.

E. Ongoing assessments that may impact the safety or ethics of the study.

The research team is active in clinical pain research and will continue to monitor the literature, attend national and international conferences, and consult with colleagues to assure that we are aware of any emerging data that may impact the safety or the ethics of the study.

F. Advanced plans for interim/futility analysis

One focus of the investigator meetings will be to continuously monitor and develop strategies to prevent adverse reactions, monitor the research staff, and protect data integrity. Accrual data will be reviewed by the team and the UTHealth IRB. The study team will make amendments to the protocol should accrual fall below 15% of the target or should drop-outs exceed projections by 15%.

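### Adverse-event questions are scheduled only at stimulation sessions, so harms in the three follow-up months, or after early stopping, are recorded only if volunteered

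*Combined protocol and SAP*

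**What the plan says.** Three places set out when participants are asked about harm, and they agree.

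- B1. Monitoring study safety: "At each stimulation, participants will be asked to report any adverse events they have experienced".
- Study Procedures, Acceptability items: side effects are rated after every session, first with an open question and then against a list that includes headache and mood change.
- Study Procedures, schedule table: the side-effects row has 15 marks, one for each of 15 sessions, and none for M1 to M3.

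After treatment, the contacts are by telephone. The table note says "Each month for three months post-intervention, participants will complete a follow-up telephone" contact, and gives its content as clinical pain intensity. The table marks NRS and WOMAC at these calls and no safety item.

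The same protocol expects harm data to keep arriving. Under B1 the investigators meet monthly to review data collected from participants on "any serious health events that caused them to seek medical attention and if any of these resulted in hospitalizations overnight". Section C, Adverse event reporting, counts a hospital admission as serious. It also gives an unscheduled route: "Study participants will be encouraged to immediately report any 'emergencies or events' by calling the study contact number". Staff who learn of an event must tell the principal investigator at once, and all reported events are logged.

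**The concern.** The monthly review is meant to draw on participant reports of medical attention and overnight hospitalisation, but no scheduled contact after the last session is specified to collect them. The same holds for a participant who stops stimulation early: the question is tied to the session, so it ends when the sessions end, and the protocol describes no other scheduled adverse-event contact for that person.

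What is at stake is how far the follow-up counts can be trusted. A count that depends on volunteering is likely to be too low, because a participant may not connect a later hospital stay or change of mood with the study. It is also hard to compare between arms, since willingness to report need not be equal in the two. The absence of a call cannot be read as the absence of an event. This bears on what the Safety Monitoring Committee and the funder see, and on the expectation in General Information that home use is safe with few side effects. The primary NRS analysis is not affected.

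**Working it through.** **Inputs**

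- Time on study (title-page summary): "Four months including follow-up assessments".
- Lead-in (Study Procedures, table note): "The baseline visit will occur 3 to 7 days prior to the tDCS intervention".
- Treatment, three-week text (Study Procedures): "Participants will do self-administered tDCS at their home or private room for three weeks (Mondays-Fridays"). Monday of week 1 to Friday of week 3 is 19 days; three full weeks are 21.
- Treatment, two-week text (Study Design): "20 minutes per session daily for 2 weeks (Monday to Friday"). Monday of week 1 to Friday of week 2 is 12 days. The two texts conflict and must be reconciled, so both are carried through.
- Follow-up (table note): three months, taken as 90 days or as 3 × 365.25/12 = 91.3 days.

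**Step 1: reproduce the stated duration.** Total = lead-in + treatment + follow-up, divided by 30.44 days per month.

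- Three-week text: shortest 3 + 19 + 90 = 112 days = 3.7 months; longest 7 + 21 + 91.3 = 119.3 days = 3.9 months. This agrees with the stated four months after rounding.
- Two-week text: shortest 3 + 12 + 90 = 105 days = 3.4 months; longest 7 + 12 + 91.3 = 110.3 days = 3.6 months.

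**Step 2: share of time in follow-up.** Share = follow-up days / total days.

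| Treatment text | Lowest share | Highest share |
|---|---|---|
| Three weeks | 90/(7 + 21 + 90) = 90/118 = 76% | 91.3/(3 + 19 + 91.3) = 91.3/113.3 = 81% |
| Two weeks | 90/(7 + 12 + 90) = 90/109 = 83% | 91.3/(3 + 12 + 91.3) = 91.3/106.3 = 86% |

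Taking the stated durations at face value gives 3/4 = 75%. Follow-up is most of the time on study in every variant.

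**Step 3: contacts with and without the question.**

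| Contact | Scheduled content on harm |
|---|---|
| Sessions 1 to 15 | Adverse-event question and side-effects questionnaire |
| Clinic testing visits | Staff monitor for events; no question specified |
| M1, M2, M3 calls | None; NRS and WOMAC only |

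The right-hand columns of the table look displaced by one in the text available here. The reading does not depend on their alignment, because the side-effects row has exactly as many marks as there are sessions. At most 120 × 3 = 360 calls take place without the question. If the 10% attrition assumed under Statistics all fell before M1, 108 × 3 = 324 would remain.

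**Step 4: set demand against supply.** B1 asks the monthly review to consider medical attention and overnight hospitalisation. WOMAC, as the protocol describes it, scores osteoarthritis symptoms, and NRS scores pain. Neither supplies those data.

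**The case against.** The strongest reply is that the protocol has other routes. B1 speaks of participant data on serious health events without limiting them to the treatment period, so the team is committed to having such data; what is missing is when and how they are obtained. The manual of procedures promised under Data quality control may say. The monthly calls are staff contacts, and an event mentioned on one must be passed on and logged. Participants are told to phone in, and the consent form is to repeat this. The device is classed as non-significant risk, discomfort is said to pass quickly, and no objective is a three-month rate of serious events. Share of calendar time is also not share of risk.

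Much of this stands, and it rules out some tempting stronger readings. A reader might infer that follow-up has no safety reporting, that nobody will ask, or that the trial cannot report follow-up events. The documents do not support that: a phone-in route and a duty on staff exist, and B1 implies some collection. A reader might also infer that delayed effects of the final session can never be picked up. That is not established either. Staff monitor testing visits, and the displaced table does not settle whether the last testing visit falls on or after the day of session 15.

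The reply does not remove the gap. Every route that the protocol specifies for follow-up depends on the participant raising the event. The manual's announced scope does not mention adverse events in follow-up, and the protocol's schedule is where such a question should appear.

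**Conclusion.** The point holds as a gap in scheduled ascertainment. Active adverse-event questions are placed only at stimulation sessions. For about three of the four months on study (76-81% of the time on the three-week text, 83-86% on the two-week text), and for anyone who stops stimulation early, events are captured only if volunteered, as far as the protocol specifies. Follow-up counts would probably be incomplete and not reliably comparable by arm, and the monthly review would lack a defined source for data it is meant to use.

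This rests on reading the table and its note as the full content of the calls, and on no unseen document adding a question. The percentages assume the lead-in, treatment and follow-up lengths shown above; the conclusion does not change across them. The number of events that would be missed cannot be estimated, because the documents give no event rate. The device's risk class and the unaffected primary endpoint keep this to a change that should be made rather than one on which the trial depends.

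**What to change.** At each M1, M2 and M3 call, after NRS and WOMAC so that those ratings are not influenced, ask the open adverse-event question used at sessions. Add two items covering the time since last contact: whether medical attention was sought, and whether there was an overnight hospitalisation. Mark these cells in the Study Procedures schedule, apply the same questions to participants who stopped stimulation early, and state that adverse-event collection runs from consent to M3. Reconcile the two-week and three-week treatment texts in the same amendment, so that the start of follow-up is unambiguous.

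The cost is a minute or two on calls already planned, one short form and a small amendment. The downside is that more unrelated events will be logged and classified.

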## B2. Minimizing research-associated risk.

Location of data collection. All procedures involving human participants will be performed at the PI's laboratory at UTHealth.

Storage of collected data. All electronic data will be stored in password-protected, secured computer systems. Only the participant's study identification number will appear on any data forms. Only research team members will have access to the completed data forms and electronically stored data. All data will be considered part of the participant's confidential record. Data collected from research participants will be stored in a secured, password-protected computer file. All paper data (e.g., participant contact information, consent forms, etc.) will be placed in a locked file cabinet within 24 hours of their acquisition as designated by the study's research assistant. All data will remain confidential.

Data entry requirements. The data entry system will require a login identification and password to gain access to the data. Where appropriate, validation and range rules will be applied to the actual entry fields. Only the PI and designated research staff will be able to view the data in its raw state.

Data management and analysis. Our research team has substantial experience in the design and implementation of data management procedures that provide accurate recording and storage of data, participant confidentiality, and timely analysis. Based on our experience, we believe that the major data management and analysis needs for the proposed project can be met by using a high-end PC, equipped with SPSS and SAS for Windows and appropriate spreadsheet programs. All data files will be automatically backed up daily. [name], the study statistician, will coordinate data management and analysis.

Data quality control. All staff involved in data collection will be trained and certified to ensure their competence and re-certified periodically throughout the study, as we have done in similar trials. Data will be collected and numerically coded using pre-tested electronic entry forms. Every effort will be made to ensure that missing data are kept to a minimum. Data entry programs with range checking and response validation will be used for all data entered. The research assistant will be trained to avoid omissions in data entry, and computer entry protocols will be programmed to avoid accidental skipping of question items. As we have done in prior studies, we will develop a manual of procedures during the initial study start-up period that explicitly describes the specific procedures related to intervention delivery, data collection, and quality assurance.

Measurement and reporting of participant accrual and adherence to eligibility criteria. The rate of participant accrual as well as adherence to inclusion/exclusion criteria will be reviewed weekly during the recruitment phase and then every month to assure that participants meet the eligibility criteria and ethnic diversity goals outlined in the grant proposal.

Final storage of paper data. All paper data (e.g., consent forms) will be housed at a facility that specializes in the storage of medical/research information. The destruction date of these files will be at least 7 years from the termination of the study and will be authorized by the PI.

Access to cleaned computer data. Once the study is complete and all data have been collected, entered, and passed the audit process, the data will be available to the PI and his designates for analysis. Only the PI can give permission for the release of aggregated study data. No confidential information may be released without the express written consent of the study participants. Only copies of the finalized data will be released. The original data file will remain in its pristine state.

B3. Protecting the confidentiality of participant data. Confidentiality will be maintained by assigning each participant a number, which will be used in all data tabulation and subsequent publications. The list linking this number to the participant's identity will be maintained in a password-protected data file, accessible only by authorized research personnel associated with the human testing components of this project. The PI will oversee the compliance of the study, maintaining strict adherence to the requirements of the law, UTHealth and federal regulations, research protocols, and health information security. Only trained research team members designated in the IRB-approved study protocol will collect data. Research Electronic Data Capture (REDCap; <http://www.project-redcap.org>) will be used to capture and store participant data, and the data will be stored on the secure data file server at UTHealth, accessible only by research team members via an encrypted and password-protected computer. All research data will be labeled using the participant's unique identifier. No name or other identifying information will be used on research data. All paper data (e.g., participant contact information, consent forms) will be placed in a locked file cabinet at the UTHealth Cizik School of Nursing within 24 hours of their acquisition.

